1 LIST OF ABBREVIATIONS

ABL	Abelson murine leukemia
AE	Adverse Event
ALK	Anaplastic Lymphoma Kinase
ATP	Adenosine Triphosphate
AUC	Area Under the plasma Concentration-time curve
BCR	Breakage Cluster Region
cfDNA	cell free DNA
CTCAE	Common Terminology Criteria for Adverse Event
c-Met	Mesenchymal-epithelial transition factor
CYP	Cytochrome P450
DCR	Disease Control Rate
DR	Duration of Response
EML4	Echinoderm Microtubule-Associated Protein-Linked 3
EORTC QLQ-C30	European Organization for Research and Treatment of Cancer Quality of Life Questionnaire Core 30
FDA	Food and Drug Administration
HDFE bottle	High Density Polyethylene Bottle
HGF/R	Hepatocyte Growth Factor/Receptor
INR	International Normalized Ratio
IRR	Independent Radiology Review
KRAS	Kirstin Rat Sarcoma
MedDRA	Medical Dictionary for Regulatory Activities
ORR	Objective Response Rate
OS	Overall Survival

PFS	Progression-Free Survival
PRO	Patient Reported Outcome
QLQ-LC13	Quality of Life Questionnaire Lung Cancer module 13
QOL	Quality of Life
QT	Time from the beginning of the QRS complex to the end of the T wave in the electrocardiogram
QTc	QT interval, Corrected for heart rate
RECIST	Response Evaluation Criteria in Solid Tumors
ROS1	c-ROS oncogene 1, receptor tyrosine kinase
RT-PCR	Reverse Transcription Polymerase Chain Reaction
TTR	Time to Tumor Response
VEGF	Vascular Endothelial Growth Factor
VHL	Von Hippel-Lindau

2 RESPONSIBLE PARTIES

The Precision Medicine Center of Excellence of Pfizer Chile (CEMP in Spanish), based in Santiago, Chile will be responsible for the execution of the non-interventional protocol.

The mission of the Center (CEMP) is to deliver technical and operational excellence in Precision Medicine R&D and molecular diagnostic development in Latin America for the benefit of cancer patients all over the world.

The other involved parties will be the hospital Centers that will be providing samples, the diagnostics test providers (Vysis ALK Break Apart FISH or Ventana ALK IHC) and the sequencing providers both in Chile and Brazil.

Their main responsibilities will be the following:

CEMP, through CRO ICON, will be responsible for sample collection and transportation from hospital centers to the FISH/Ventana ALK test providers, the sequencing providers and/or CEMP facilities. Thus, CEMP will receive clinical data informed consents, tissue and blood samples coming from hospitals, and data results of FISH/Ventana ALK and NGS from research centers.

In Brazil, AC Camargo Cancer Center (ACC), as a FISH/Ventana ALK and NGS sequencing provider, will perform nucleic acid extraction from both kind of samples (tissue and blood). ACC will also perform genomic analysis using a PGM device. Biondata (.vcf and .pdf files) coming from the sequencers will be processed and raw data will be supported in a Data Center. ACC will be responsible for the storage of the remaining tissue and the nucleic acid from blood in Brazil.

In Chile, CEMP Genomic Laboratory and the sequencing center Genoma Mayor will perform nucleic acid extraction from both kind of samples (tissue and blood). Also, they will perform genomic analysis using a PGM device and process the biondata coming from the sequencers and will store the raw and processed data accordingly. CEMP will be responsible for the storage of the remaining tissue and the nucleic acid from blood in Chile.

In both countries, the NGS service providers (ACC, Genoma Mayor and Genomic Laboratory at Pfizer) will work as a parallel sequencing facility.

The reference hospital centers will be responsible for collecting the patient identification according to the inclusion criteria, gathering the clinical data and due diligence to obtain the informed consent from patients. They will obtain and process the tissue and blood samples according to guidelines and perform the histopathological analysis. Some of the hospital Centers will perform the FISH/Ventana ALK test if technology and expertise is available. If not, samples will be sent to the designated FISH/Ventana ALK provider in Brazil or Chile.

PPD

090177e191f145b3\Approved\Approved On: 25-Sep-2019 09:08 (GMT)

ABSTRACT

Non-Interventional Multi-Center Study for Molecular Diagnostic Technologies Validation in NSCLC Patients

To identify patients who can respond to targeted therapies, it is imperative that new molecular diagnostics be developed and deployed.

The research lines planned for the CEMP-Chile are aimed at data generated to validate NGS (Next Generation Sequencing) and blood detection for ALK and/or ROS translocations. These patients may be eligible for ALK and/or ROS inhibitor treatment; however treatment and follow-up on care is out-of-scope of this protocol.

Study Objectives and Endpoints:

Primary objective

- To determine concordance between the Vysis ALK Break Apart FISH test or the Ventana ALK IHC test and ThermoFisher NGS technology.
- Validation of more sensitive, less invasive and state of the art screening platforms for NSCLC.

CCI [Redacted text block]

090177e191f145b3\Approved\Approved On: 25-Sep-2019 09:08 (GMT)

Study Design

This is a non-interventional multi-center diagnostic study to validate novel diagnostic technologies, such as Next Generation Sequencing (NGS) from both tissue and blood compared to the current gold standard tests.

As a non-interventional study, patients will not be treated or affected as part of the protocol.

This study will determine the correlation between the Vysis ALK Break Apart FISH test or the Ventana ALK IHC test of NSCLC tumors and next generation sequencing NGS analysis from tissue and blood derived nucleic acids. The study involves the collection and analysis of FFPE tumor tissue and blood of NSCLC patients to be analyzed with a Thermo Fischer NGS Oncomine fusion panel assay.

A positive correlation with these novel technologies will mean an efficient, more accurate test, which could impact a greater number of cancer patients around world.

The endpoint of this Project will be to analyze 30 positive ROS1 and 120 positive ALK samples to validate the diagnostic method.

Given an estimated prevalence of ROS1 at 1-2% and ALK at 3-5% for NSCLC, an initial set of 1000 patients will be screened. An interim analysis will be performed at the first 1000 NSCLC samples to evaluate prevalence rates (tentatively 10 ROS1+ and 40 ALK+).

For the majority of molecular tests, it is expected that at least 50 positive patient samples be utilized for validation, and ideally at least 10 positives representing each variant being detected¹. Given the low prevalence of ROS1 which has 16 unique variants and recent analysis demonstrating that in 30 ROS1+ patient samples, there is representation of the 3 dominant variants suitable for analytical validation², it is necessary to screen at least 3000 NSCLC samples for identifying positive samples for both ROS1 and ALK that should be sufficient for analytical validation of the NGS platform. If anticipated prevalence rates at the 3000 sample mark do not align with determined prevalence rates at this stage and/or 30 positive ROS1 and 120 positive ALK samples are not obtained, an additional 3000 patients will be screened for a potential total of 6000 patients. The overall screening will occur at 3 or more sites. Patients will only participate in the study for the initial sample collection period.

The study will be completed in approximately 48 months.

Study Treatment

None.

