6 RESEARCH QUESTION AND OBJECTIVES

This investigation intends to validate molecular diagnostics technologies on ALK+/ROS1+ NSCLC tumor diagnostic; more accurate and precise methods than the existing companion diagnostics (FISH Vysis ALK Break Apart FISH test or the Ventana ALK IHC test).

CEMP Genomic Laboratory together with its sequencing providers (ACC in Brazil, Genoma Mayor in Chile) will process NGS data from tissue and blood and compare it against histopathological and FISH/Ventana ALK results. With this comparison CEMP will be able to determine if NGS technologies are suitable to be considered as accurate diagnostic methods.

The main question that will be addressed in this project is the significant global demand to develop improved molecular diagnostics for cancer, for both translational/clinical applications, as well as companion diagnostics to personalize oncology medicines, in order to increase the overall effectiveness of therapies to patients which may benefit the most, with significant value add to both payers (public healthcare and/or healthcare insurance) and drug manufacturers.

Accordingly, next generation molecular diagnostics should leverage scientific advancements to become less invasive, require less amount of patient tissue for testing and of greater sensitivity to cancer-specific genetic indicators, whether inherited, mutated, or transcribed.

The primary disease focus of this project is to examine novel technologies for NSCLC patient screening for detection of ALK and ROS1 positive patients.

The project will address this technical issue through two research lines:

- 1) Development of an ALK/ROS fusion specific next generation sequencing panel;
- 2) Detection of tumor-derived nucleic acids in the blood of patients diagnosed with NSCLC.

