7.1 Study design

This is a non-intervention multi-center study where tissue and blood of NSCLC patients will be collected. Patients will not be treated as part of this protocol and will only participate in the study for the initial samples and clinical parameters collection period.

Up to 6000 patients are expected to be screened in the study overall at 3 or more sites.

Samples should include:

1. Archived or tumor tissue as formalin-fixed paraffin-embedded (FFPE) tissue block or 10 unstained slides containing serial 5-micron tumor tissue sections.
2. Blood samples collected in the provided StepCheck tubes. One 8ml tube for DNA collection, one 8mL tube for RNA collection.

The study will evaluate the strength of NGS technology as diagnostics methods for ALK+ and or ROS1+ tumors.

The strength of the study is based on the fact that NGS technology has an adequate sequencing quality ($Q>30$) and coverage, which ensures the accuracy of results. Given the low prevalence of ALK and ROS rearrangements, it is necessary to sample up to 6000 samples to obtain at least 30 ROS1+ for adequate concordance against other platforms. This is critical for the diagnostic evaluation results, making it eligible as a good diagnostic method.

Besides this, the clinical data will be correlated to the NGS data. This will provide demographics correlations and give information about the incidence of the markers in the Chilean and Brazilian people.

The study will be completed in approximately 48 months.

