6 ENDPOINTS AND COVARIATES

a. Primary Endpoint.

- **Primary endpoint 1:** Obtaining results / diagnosis of NGS and Ventana for the ALK biomarker.
- **Primary endpoint 1:** Analysis of NGS y Ventana for ALK.

b. Secondary Endpoints

Secondary endpoint 1: PE1 in prospective and retrospective patients.

Secondary endpoint 2: PE1 in smokers and non-smokers.

Secondary endpoint 3: PE1 depending on the location, stage and histological classification of the biopsy

Secondary endpoint 4: PE1 in patients of different gender and age.

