8 STATISTICAL METHODOLOGY AND STATISTICAL ANALYSES

8.1 STATISTICAL METHODS

a. Sample Size Calculation:

The sample size can be estimated according to a desired sensitivity or specificity, and the choice of the N obtained will be defined by privileging to maximize the sensitivity (cut-off value defined > 0.8). The sample size necessary to demonstrate hypothesis will be defined. This calculation will be made at each of the interim analysis, to evaluate the total number of patients to be recruited. The sample size calculation formulas are defined

Formula of the sample size calculation dependent on Sensitivity

$$N(sN) = \frac{TP+FN}{P}$$

Where,

$$TP+FN = z^2 \times \frac{(SN(1-SN))}{W^2}$$

TP : Prevalence of ALK rearrangements in the population and / or in the data set of the interim analysis.

SN : Minimal acceptable sensitivity

W : Desired confidence interval, also called α (here a 99 % is desired)

z : Constant dependent on the desired confidence interval, this value is obtained from the table of the normal distribution. For a 95 % confidence interval the value of z is 1.96, and for a range of 99 %, it is 2.58.

i. Formula of the calculation of the sample size dependent on the Specificity:

$$N(sP) = \frac{FP+TN}{(1-P)}$$

Where,

$$FP+TN = z^2 \times \frac{(SP(1-SP))}{W^2}$$

P : Prevalence of ALK rearrangements in the population and / or in the data set of the interim analysis.

SP : Minimal acceptable specificity

W : Desired confidence interval, also called α (here a 99 % is desired)

z : Constant dependent on the desired confidence interval, this value is obtained from the table of the normal distribution. For a 95 % confidence interval the value of z is 1.96, and for a range of 99 %, it is 2.58

b. Concordance test:

i. Test type:

The agreement between Ventana ALK and NGS assay for ALK will be evaluated based on the Binary Qualitative type (Two tails), where the results can only have two values (concordance, discordance). The following metrics will be evaluated from the results:

- *Sensitivity:* $\frac{TP}{(TP+FN)}$
- *Specificity:* $\frac{TN}{(TN+FP)}$

- *Precision: PPV* = $\frac{TP}{(TP+FP)}$
- *Accuracy*: $\frac{TP+TN}{TP+TN+FP+FN}$
- Limit of detection (LOD): They will be established a priori by the reference values delivered by Thermo Fisher. After the interim analysis, these will be re-evaluated and / or modified. Among the influential values in the limits of detection are: the coverage

ii. Concordance methods:

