8.2.2 Analyses of endpoint

Not Applicable

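### The visible protocol endpoint is a sample count and the SAP primary endpoint is obtaining and analysing results; neither contains an agreement measure, and the planned ALK test cannot supply one

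*Protocol*

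**What the plan says.** The protocol abstract, under Study Design, puts the endpoint as a number of positive samples: "The endpoint of this Project will be to analyze 30 positive ROS1 and 120 positive ALK samples to validate the diagnostic method". Protocol 7.1 says that up to 6000 samples are needed to reach at least 30 ROS1+ for adequate concordance with other platforms, and continues: "This is critical for the diagnostic evaluation results, making it eligible as a good diagnostic method".

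SAP section 6a lists two items, both labelled Primary endpoint 1: "Obtaining results / diagnosis of NGS and Ventana for the ALK biomarker" and "Analysis of NGS y Ventana for ALK". The four secondary endpoints repeat the first primary endpoint in subgroups. The SAP section headed "8.2.2 Analyses of endpoint" is marked as not applicable.

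Agreement appears elsewhere:

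- The first primary objective in the protocol abstract is "To determine concordance between the Vysis ALK Break Apart FISH test or the Ventana ALK IHC test and ThermoFisher NGS technology".
- SAP 4.1 sets a hypothesis for ALK and SAP 4.2 a threshold of P ≤ 0.05.
- SAP 5 compares NGS with Ventana in Ventana-positive patients and uses Ventana-negative patients for false positives.
- SAP 8.1 lists sensitivity, specificity, PPV, accuracy, PPA, NPA, McNemar's test and kappa.
- The only numeric performance level is a sensitivity cut-off above 0.8. It stands in the sample-size part of SAP 8.1, where the formula uses "SN : Minimal acceptable sensitivity".

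**The concern.** Protocol section 6 says that the comparison should let the sponsor "determine if NGS technologies are suitable to be considered as accurate diagnostic methods". That is a yes-or-no conclusion about the assay. The visible endpoints turn on recruitment, prevalence and the existence of two results. How often NGS finds the reference positives, or calls reference negatives positive, enters none of them.

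Several agreement measures are planned, but none has a level at which NGS counts as validated. The choice of measure, and of what is good enough, could then be made after the results are known. An assay could be reported as having met its validation endpoint while missing many ALK+ tumours.

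**Working it through.** **1. The plan's own count.** Expected positives = patients × prevalence. With 3000 patients, 3000 × 1% = 30 ROS1+ and 3000 × 4% = 120 ALK+. With 1000, the result is 10 and 40, as the abstract states. The target follows from prevalence and screening alone.

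**2. What moves the count endpoint.** Assume that positives are set by the reference test and that every positive is evaluable. The binomial probability of at least 120 ALK+ among 3000 is 0.001 at 3% prevalence, 0.513 at 4% and 0.996 at 5%. At 6000 patients and the lowest anticipated prevalences (ROS1 1%, ALK 3%), P(at least 30 ROS1+) × P(at least 120 ALK+) = 0.99999, treating the two as independent. NGS sensitivity is in none of these expressions. Among 120 ALK+, NGS could detect 114 (95%; Wilson 95% interval 0.895 to 0.977), 60 (50%; 0.412 to 0.588) or 0 (0 to 0.031), and the samples would still have been analysed and the results obtained.

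**3. Whether the planned test fills the gap.** SAP 4.1 takes as its null hypothesis that the two methods' results are not equal. McNemar's test in SAP 8.1 has the null p_b = p_c, and a significant result there means that the marginal proportions differ. A small P value therefore rejects McNemar's null but cannot support the SAP's alternative of equality. The SAP statistic is X² = (|b − c| − 1)²/(b + c). Two tables with 3000 patients and 120 Ventana-positive:

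| | Poor assay | Good assay |
|---|---|---|
| Detected / missed | 60 / 60 | 118 / 2 |
| False positives | 60 | 12 |
| Sensitivity | 50% | 98% |
| X² | 1/120 = 0.008 | 81/14 = 5.79 |
| P | 0.93 | 0.016 |
| Kappa | 0.48 | 0.94 |

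For the poor assay, P_o = 2880/3000 = 0.96, P_e = 0.04² + 0.96² = 0.9232, and kappa = 0.0368/0.0768 = 0.48. For the good assay b + c = 14, below the 25 at which the SAP calls for a modified method; an exact binomial test gives P = 0.013, so the reading is the same.

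**4. What a rule on the intervals would require.** Lower Wilson limit = [p + z²/2n − z√(p(1−p)/n + z²/4n²)]/(1 + z²/n). With n = 120, z = 1.96 and p = 105/120 = 0.875, this is (0.875 + 0.0160 − 0.0613)/1.0320 = 0.804; 104/120 gives 0.794. So 105 detected is the smallest number with a 95% lower limit above 0.8. With z = 2.58 (99%), 107/120 gives 0.797 and 108/120 gives 0.807, so 108 are needed.

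Chance of meeting each rule, binomial with n = 120:

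| True sensitivity | At least 105 (95%) | At least 108 (99%) |
|---|---|---|
| 0.70 | <0.0001 | <0.0001 |
| 0.80 | 0.022 | 0.003 |
| 0.85 | 0.267 | 0.075 |
| 0.90 | 0.856 | 0.576 |
| 0.95 | 0.9997 | 0.993 |

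The planned 120 ALK+ can therefore separate a poor assay from a good one, if a rule is written.

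**5. Why specificity is needed too.** An assay that calls every sample positive detects 120/120, with a 95% lower limit of 1/(1 + 3.84/120) = 0.969. It passes any rule on sensitivity alone.

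**The case against.** The strongest reply is that the plan does not ignore agreement. Concordance is a primary objective, the ALK hypothesis and P value threshold exist, and the measures are listed. With 60 of 120 missed and no false positives, the SAP statistic is (60 − 1)²/60 = 58, P about 3 × 10⁻¹⁴, and the SAP would read the methods as different. With 35 false positives it is still significant (24²/95 = 6.06, P = 0.014). This stands: a reader might infer that an assay missing half the ALK+ tumours would go unnoticed, and the documents do not support that in general. The test fails to flag it when misses and false positives roughly balance, and it flags a good assay when they do not.

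Second, independence from NGS performance is conditional. The abstract does not say which test defines a positive. For ROS1, protocol section 5 says only that a reference test may be necessary, and SAP 2.2 plans concordance for ALK alone. If ROS1+ are found by NGS, with no false calls, P(at least 30) at 6000 patients and 1% prevalence is about 1.00 at sensitivity 1, 0.52 at 0.5 and 0.006 at 0.3. SAP 7 also removes samples with insufficient nucleic acid or failed RNA quality control from the primary analysis, so 0.99999 is an upper figure. The condition must be stated. Even then, a count of positives does not limit missed cases or false positives.

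Third, a block is redacted under the abstract's objectives and endpoints, so nobody can say that the protocol has no agreement endpoint. The sentence quoted from the abstract and SAP section 6 are not redacted.

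Fourth, determining concordance can be an estimation aim, which needs no pass mark. That is fair for the objective alone, but protocol section 6 goes further and wants a decision on suitability.

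**Conclusion.** The concern holds for the endpoints as visibly written. The abstract's endpoint is a count, the two SAP lines require only that results be obtained and analysed, and none names an agreement measure. If positives are those of the reference test, all are met at any NGS sensitivity from 0 to 1. The planned ALK measures are not tied to the endpoint. McNemar's test cannot show validation, because its null is the reverse of the SAP's and it gives p = 0.93 at 50% sensitivity in the balanced example. The 0.8 sensitivity minimum is never compared with an estimate.

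A reader might also infer from protocol 7.1 that eligibility as a good diagnostic method rests on collecting 30 ROS1+ alone. The text does not go that far, since it gives adequate concordance as the reason for the number. The fault there is that it never says what concordance would be adequate.

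The pass probabilities assume 120 evaluable ALK+ and a reference test taken as true. Taking 0.8 as the pass level joins the SAP's cut-off with its term for minimal acceptable sensitivity; the documents do not themselves make it a success criterion.

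**What to change.** - **SAP 6a:** replace both Primary endpoint 1 lines with PPA (sensitivity) and NPA (specificity) of NGS against the ALK reference test, by the SAP 8.1 formulas, each with the Wilson interval named in protocol 7.4.
- **Validation rule for ALK:** base the conclusion on those intervals and not on the McNemar P value. The lower limit for sensitivity must exceed 0.8, and the lower limit for specificity must exceed the sponsor's minimal acceptable specificity. SAP 8.1 defines that quantity but gives no value, so the sponsor must state one.
- **Confidence level:** state one level for both limits. Protocol 7.4 uses 95%, while SAP 8.1 says that 99% is desired. The choice decides between 105 and 108 detected of 120.
- **Protocol abstract and 7.1:** call 30 ROS1+ and 120 ALK+ the recruitment target, not the endpoint or the ground for eligibility.

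No new data or method is needed. The costs are real, however. The study can now fail its primary endpoint. Protocol 7.6 requires an amendment for major changes to primary endpoint definitions, and protocol 8.3 then requires IRB/IEC approval. SAP version 2.0 is dated 10 July 2019, after the planned end of data collection on 30 June 2019. A threshold added after data have been seen must be reported as post hoc.

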3 AMENDMENTS AND UPDATES

None.

4 MILESTONES

Milestone	Planned date
Start of data collection Initiation of NSCLC FFPE tissue collection	June 30, 2015
End of data collection Completion of 6000 FFPE samples, 6000 blood samples	June 30, 2019
Interim study report Data analysis of the first 1000 samples processed by NGS will be assessed	October 31, 2016
Interim study report Data analysis of the first 3000 samples processed by NGS, and first 1000 blood samples will be assessed	October 31, 2017
Final study report Data analysis of the last 6000 samples processed by NGS, 3000 blood samples will be assessed	December, 31, 2019

